Cryoanalgesia has been used to treat pain syndromes including facial neuralgias and peripheral neuropathies.¹² In the 1980s, this technique was applied for postoperative pain control in patients with thoracotomy with satisfactory improved pain control without adverse events.^{13,14} The Food and Drug Administration (FDA) approved

the first commercially available cryoablation probe (CryoICE®, AtriCure, Mason, OH), which made the cryotherapy more applicable. Postoperative pain management of thoracoabdominal incisions is the most invasive incision and pose a difficult challenge to manage pain control. Thus, we propose a pilot study to investigate the effectiveness of intercostal nerve cryoablation for postoperative pain control. This pilot study will lead to an estimate on its efficacy and utilization as an option for the postoperative pain management using the cryoablation. We will perform a larger prospective randomized study if this pilot study demonstrates the efficacy of the procedure.

VII. PRIMARY OBJECTIVES

The primary objective of the study is to prove the feasibility of intercostal nerve cryoablation in postoperative pain control both in magnitude and duration in patients undergoing thoracoabdominal incisions for the descending or thoracoabdominal aortic aneurysm repair.

Specific assessment tools that will be used in our study are:

1. Numeric Pain Scale (NPS): The NPS measures the intensity of pain. It consists of an 11-point scale from 0-10, where 0 means no pain and 10 means the most intense pain imaginable. Patients verbally select a value that correlates to the pain experienced by them. A written form can also be used. The NPS has good sensitivity and has a good capacity of producing data that can be statistically analyzed.^{15,16,17,18}

2. Brief Pain Inventory (BPI): The Brief Pain Inventory is a medical questionnaire used to measure pain, developed by the Pain Research Group of the WHO Collaborating Centre for Symptom Evaluation in Cancer Care. Although the BPI is derived from the NPS it is more comprehensive and expanded. Besides assessing pain intensity, it assesses how much the pain is affecting their lives. The BPI is a powerful tool and, having demonstrated both reliability and validity across cultures and languages, is being adopted in many countries for clinical pain assessment, epidemiological studies, and in studies of the effectiveness of pain treatment.^{19,20}

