The target population of our study will be comprised of patients that are 18 years-old and above that present to our group at the McGovern Medical School at UTHealth and will require thoracoabdominal incision for the descending/thoracoabdominal aortic aneurysm repair. Our plan is to enroll 20 patients over a period of 6 months.

Inclusion/Exclusion Criteria

Patients will be eligible for the study if:

- 18 years-old or older, and
- Descending/thoracoabdominal incision is planned
- There is reasonable expectation that the patient will be extubated within 48 hours after surgery

Patients will be excluded from the study if:

- The patient has a known allergy to morphine or any opioid
- The patient has a known chronic pain disorder or takes daily opioid medication > 1 month prior to surgery
- The surgeon/anesthesiologist concludes that the period for intubation will be likely be for more than 48 hours after surgery There is anticipated difficulty communicating pain status due to language or other barriers at the investigator discretion.

Protocol Deviation:

It will be considered a protocol deviation if patients receive, during the first three days after surgery, any type of analgesic other than opioids.

Withdrawal criteria:

- Voluntary: patients who had consented and enrolled in the trial will maintain their right to withdraw at any point during the study as explained in the informed consent.
- In case of unexpected/unpredicted

X. STUDY DRUGS

CryoICE® CRYO2 cryoablation probe (AtriCure, Inc) is an FDA-approved device for the use of intercostal nerve cryoablation. Subjects will be randomized into two groups: Group A will receive the study procedure, intercostal nerve cryoablation using CryoICE® CRYO2 cryoablation probes (AtriCure, Inc) to intercostal spaces 4th to 10th in thoracoabdominal aortic repairs and 4th to 8th in descending thoracic aortic repair cases. This procedure will be performed under electromyography to confirm the successful ablation of the nerve. Group B will not receive cryoablation but will obtain electromyography to evaluate as the control.

Both patient groups will receive intraoperative local analgesia infiltration with bupivacaine liposomal injectable suspension (Exparel®, Pacira Pharmaceuticals) and patient-controlled analgesia (PCA) postoperatively.

XI. STUDY SCHEDULE

Expected start date: Jan 1st, 2019

Expected end-date for enrollment: June 30th, 2019

Length of enrollment for each patient: 6 months

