Length of follow-up for each patient: 6 months

Expected end-date of study: January 31st, 2020

XII. STUDY DESIGN/METHODOLOGY

This will be a single institution, prospective, single-blinded, randomized, controlled effectiveness study with 2-armed parallel-group sequential design to assess the efficacy of intraoperative intercostal nerve cryoablation in postoperative pain control when compared to our current standard care, local anesthesia infiltration of Exparel®.

Screened patients meeting the eligibility criteria will be randomized into one of the two study groups. Both patient groups will receive intraoperative local analgesia infiltration with Exparel® prior to wound closure and patient-controlled analgesia (PCA) postoperatively. Each patient will choose whether or not they will use PCA. The first group (A) of patients will receive intraoperative intercostal nerve cryoablation using CryoICE® CRYO2 cryoablation probes (AtriCure, Inc) to intercostal spaces 4th to 10th in thoracoabdominal aortic repairs and 4th to 8th in descending thoracic aortic repair cases prior to wound closure. This procedure will be performed under electromyography to confirm the successful ablation of the nerve. The second group (B) of patients will be injected with Exparel® in the surgical wound. We will obtain intraoperative electromyography to evaluate as the control.

On the screening visit, patients should present prior to surgery to receive training on the NPS and BPI and to be assessed on their preoperative baseline pain level, using BPI. This may be performed prior to surgery in the preoperative holding area, on the inpatient ward, or in the outpatient settings of the McGovern Medical School at UTHealth.

Patients from both groups will receive the same volume of diluted Exparel®, which will be given in four 20ml syringes using 22-gauge needles (266mg of liposomal bupivacaine, equivalent of one 1.3% 20ml vial of EXPAREL, diluted in 50ml of preservative-free normal (0.9%) sterile saline for a total volume of 70ml). Intercostal muscle electromyogram will be performed in both groups. Group A will have it done before and after the cryoablation. This assessment is to confirm the completeness of the intercostal nerve cryoablation, as the waveform of the electromyogram is expected to disappear after an adequate cryoablation. Group B will have the electromyogram prior to wound closure. The surgical wound length will

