7am (+/- 2 hours) of the third to fifth post-op day and as well as on their 30th and 180th post-operative days. After the 180-day follow-up and BPI reporting, the patient terminates his/her enrollment. This enrollment termination does not mean severance of the physician-patient relationship. Patients will be consented and their medical records pertinent to the study will be collected on a case report form and this information will be kept on a secured HIPAA-compliant web-accessed database. No protected health information (PHI) will be maintained on the web-accessible database.

Study Conduct

1. Screening

The research group will assess patients as possible candidates for enrollment based on the inclusion criteria and the planned surgical exposure: median sternotomy, thoracotomy, midline laparotomy, and/or thoracoabdominal incision. Once the eligibility is met, an informed written consent will be collected. A member of the research team - the PI, Co-PI, research coordinator, or nurse will obtain the consent from the surgical candidates who met the preliminary inclusion criteria. The consent process will take place either during the preoperative clinic visit, upon inpatient admission, or in the preoperative holding area. Patients will be consented before their surgical procedures and will be given the appropriate time to think and discuss with family about being part of the study. There will also be given enough time for the patients to ask questions about the protocol and research study. A copy of the signed informed consent shall be provided to the patient, a copy will be placed in the patient's hospital chart, and a copy will be kept by the research team. Medical/surgical history, vital signs measurements, drug/alcohol screening, and standard preoperative testing will also be performed as per the usual surgical practice.

2. Quality of life assessment - Brief Pain Inventory

The impact of pain on patient's quality of life will be assessed through a brief pain inventory (BPI) that should be done before surgery, at 7am (+- 2 hours) of the third to fifth post-operative day as well as on their 30th and 180th post-operative days. The BPI

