8. Termination of enrollment

Patient will be considered to have his/her enrollment terminated:

- i. After the 180-day follow-up visit, or
- ii. If follow-up is lost after several attempts to contact patient, or
- iii. If any medical/surgical/environmental condition develops that would affect or impair primary or secondary outcomes measurements results, or
- iv. If the study is terminated, or
- v. If the patient dies.

9. Termination of Study

- i. End of study period
- ii. If a clinically/statistically significant difference is achieved early during an interim analysis.

XIII. ADVERSE EVENT REPORTING

Patients enrolled in the trial will be informed to report any unwanted effect at any time during the study. Adverse effects of intercostal nerve cryoablation will be made plain to the patients during the screening/enrollment as well as in the informed consent process. Most adverse side effects are injury of the lung or other surrounding organs/tissues, which may happen if cryoablation probe is misplaced to the organ/tissue. This is extremely rare amongst trained and board-certified vascular surgeons. All the surgeons involved in our study have been extensively trained on the cryoablation technique required for appropriate use. Other adverse effects include

allodynia like-pain after the degeneration of the affected nerve is reported after cryoablation of the nerve, but this is often associated with thoracotomy procedure and not specific to the cryoablation. Safety monitoring will include assessment of:

- i. Adverse Effects (AE)
- ii. Vital Signs
- iii. Wound healing status
- iv. Scarring
- v. Cardiac monitoring

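### As written, a positive interim analysis could end follow-up of patients already randomised before day 180, in conflict with the study timeline

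*Combined protocol and SAP*

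**What the plan says.** Two adjacent lists in section XII govern stopping. Section XII.9 (Termination of Study) has two entries: the end of the study period, and "If a clinically/statistically significant difference is achieved early during an interim analysis". Section XII.8 (Termination of enrollment) gives alternative events that end a patient's enrolment. The 180-day visit is the first, and the fourth reads "If the study is terminated, or".

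Enrolment here means more than accrual. Section XI gives "Length of enrollment for each patient: 6 months" and "Length of follow-up for each patient: 6 months", and section XII says: "After the 180-day follow-up and BPI reporting, the patient terminates his/her enrollment".

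Section VII sets the primary objective, to "prove the feasibility of intercostal nerve cryoablation in postoperative pain control both in magnitude and duration". Its primary outcome measures are the AUC of the Numeric Pain Scale (NPS), the BPI and the satisfaction scale; the last two are also collected at days 30 and 180. In the follow-up list of section XII.7, those are the only scheduled pain assessments after day 5. Section XIV.A specifies one primary test, a Wilcoxon rank-sum comparison of NPS AUC over postoperative days 3 to 5.

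Section XVI allows for interim analyses within its six-month recruitment estimate. It then plans follow-up until 180 days after the last patient, with analysis when everyone's follow-up is complete. It does not say what happens after an early stop.

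**The concern.** The plan does not distinguish stopping randomisation from stopping follow-up. Applied literally, a positive interim terminates the study, and termination ends participation for everyone still in it. Days 3-5 pain is known within a week of surgery, whereas the last BPI is due six months later, so an interim on an early measure could be positive long before late data exist.

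This is separate from the missing interim boundary and alpha control: a perfectly controlled interim would have the same effect on follow-up.

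At stake is evidence on how long any benefit lasts. Section VI says a larger randomised trial will follow if the pilot demonstrates efficacy, so the pilot's late data would inform that trial, and follow-up not collected at the time cannot be recovered.

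**Working it through.** **1. Does the plan's own calendar reproduce?** Inputs from section XI: "Expected start date: Jan 1st, 2019", "Expected end-date for enrollment: June 30th, 2019", and a study end of 31 January 2020. Section XVI allows one month for analysis.

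- Recruitment window: 1 January to 30 June 2019 = 180 days.
- Last patient's day 180: 30 June + 180 days = 27 December 2019.
- Plus one month of analysis: 27 January 2020, inside the planned end.

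The calendar is consistent, and it assumes that every patient is followed to day 180.

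**2. When can the first day-180 record exist?** 1 January 2019 + 180 days = 30 June 2019, the last planned recruitment day. A stop on any earlier day finds no patient at day 180. A stop on that day finds at most one, and only if the first surgery was on 1 January.

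**3. How many records would exist at an interim stop?** Assumptions not in the plan: surgery on the day of enrolment; 20 patients evenly spaced over D days, so that patient i is treated on day t(i) = (i − 1) × D/19; and a stop 5 days after the k-th surgery, when that patient's NPS series is complete. A patient has reached day d if t(i) + d ≤ t(k) + 5.

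With D = 180 the spacing is 180/19 = 9.47 days.

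- k = 10: stop on day 9 × 9.47 + 5 = 90.3. Day 30 needs t(i) ≤ 60.3, which 7 patients meet. Day 180 needs t(i) ≤ −89.7, which none meets.
- k = 15: stop on day 14 × 9.47 + 5 = 137.6. Day 30 needs t(i) ≤ 107.6, which 12 meet. Day 180: none.

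| Stop after | With day-30 BPI | With day-180 BPI |
|---|---|---|
| 5 | 2 of 5 | 0 of 5 |
| 10 | 7 of 10 | 0 of 10 |
| 15 | 12 of 15 | 0 of 15 |
| 19 | 16 of 19 | 0 of 19 |

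**4. Sensitivity to slower recruitment.** Patients with day-180 data, by the same rule:

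| Stop after | 9 months (D = 273) | 12 months (D = 364) |
|---|---|---|
| 10 | 0 | 0 |
| 15 | 2 | 5 |
| 19 | 6 | 9 |

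A late look in a slow trial would therefore leave a few day-180 records; a look at the halfway point would still leave none.

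**5. If randomised patients stayed in follow-up.** After a stop at 10 patients, all 10 would be due both late assessments: 10 instead of 7 at day 30, and 10 instead of 0 at day 180.

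**The case against.** The strongest reply is section XVI. It mentions interim analyses and still plans follow-up to 180 days after the last patient, with analysis only afterwards. That supports an intention to follow everyone, so a reader who infers from section XII alone that the day-180 data would certainly be lost goes too far. What stands is that section XVI is a general timeline: it neither addresses an interim stop nor overrides the termination list. The two sections conflict and have to be reconciled.

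Second, the interim endpoint is unstated. Section VII also counts the late BPI and satisfaction scores among the primary measures, and section XIV.C sizes the trial on BPI. The counts above therefore hold only if the trigger is an early measure. The NPS AUC is the natural candidate, but that is an inference.

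Third, a reader might conclude that the duration question would go wholly unanswered. The documents do not support that. Duration is never defined. Section VI describes liposomal bupivacaine as acting for perhaps 48 hours, so pain on days 3 to 5 already says something about duration, and some patients would have day-30 data. The SAP also specifies no analysis of day-30 or day-180 BPI, so the late data lack a planned analysis even with complete follow-up. That is a separate gap and no reason to lose the data.

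Fourth, it is tempting to say that 0 of 20 day-180 records would be obtained. The right denominator is the patients randomised by the time of the stop; those never randomised have no late data under any wording.

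Finally, one might infer that late allodynia-like pain would go undetected. Section XIII describes it as not specific to cryoablation and follows adverse effects through clinic visits and patient contact, so that inference is not secure.

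**Conclusion.** The point holds in a conditional form. Sections XII.8 and XII.9, as written, could end follow-up of randomised patients before day 180 after a positive interim, and this conflicts with section XVI. If the interim uses the day 3-5 NPS AUC and recruitment is even over the planned six months, a stop after 10 patients leaves 7 of 10 with day-30 and 0 of 10 with day-180 BPI; a stop after 15 leaves 12 of 15 and 0 of 15. The zero at day 180 follows from the planned dates for any stop before 30 June 2019. The day-30 counts also need the even-accrual assumption.

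The loss is limited to part of the day-30 evidence and the evidence beyond it. It bears on the duration element of the primary objective without removing all information on it. The contradiction is worth resolving before any interim look.

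**What to change.** Reconcile sections XII and XVI with two sentences in an amendment:

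- In section XII.9, second entry: an interim efficacy difference stops further randomisation only.
- In section XII.8, fourth entry: after such a stop, every patient already randomised stays enrolled through the planned day-30 and day-180 BPI and satisfaction assessments.

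No new visit is needed, since these assessments are already scheduled. The cost is time: if the look falls 5 days after the last surgery, the final report waits a further 180 − 5 = 175 days for that patient's day-180 visit. On the planned dates that visit falls no later than 27 December 2019, inside the planned study end of 31 January 2020.

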will be presented in an easy to comprehend questionnaire for the patients to quantify and communicate their pain experience and how it is affecting their life. It is designed such that patients with 6th-grade education should be able to complete the questionnaire on their own. Question and answers will be provided in a check-box format. The BPI that will be used on this study will be the short version. Patients with difficulty reading or who are physically unable to complete the questionnaire will be assisted by the research team based on their verbal responses to the BPI questions.

4. Enrollment

After the screening is done, the eligibility criteria are met, and the patient is consented; the patient will be enrolled in the trial. At this point, the study coordinator/research office will be notified so that the patient can be randomly allocated to one of the study groups.

5. Randomization and Allocation Concealment

Randomization and allocation concealment will be performed via a web-based/computer generated block randomization sequence/list secured in a password-protected secure computer in the trial office accessible only to the research staff independent of the trial administration process, who are not involved in the recruitment, data collection, analysis, assessment and/or follow-up. This office/research staff will be contacted by the blinded research assistant/investigator to provide certain specific

6. Preoperative assessment

Pain assessment will be also done using the BPI form.

7. Follow-up

After the surgical procedure is done, the follow-up will be:

- i. 7am (+ or - 2 hours) of the third post-op day: the NPS and the the BPI and 5 -point scale analgesia satisfaction survey will be assessed
- ii. 7pm (+ or - 2 hours) of the third post-op day: the NPS will be assessed
- iii. 7am (+ or - 2 hours) of the fourth post-op day: the NPS and the the BPI and 5 -point scale analgesia satisfaction survey will be assessed
- iv. 7pm (+ or - 2 hours) of the third post-op day: the NPS will be assessed

- v. 7am (+ or - 2 hours) of the fifth post-op day: the NPS and the the BPI and 5-point scale analgesia satisfaction survey will be assessed
- vi. 7pm (+ or - 2 hours) of the fifth post-op day: the NPS will be assessed
- vii. 30 days after the procedure, the BPI and 5-point scale analgesia satisfaction survey will be assessed.
- xiii. Final visit, 180 days after procedure, the BPI and 5-point scale analgesia satisfaction survey will be performed.

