All items above will be closely monitored in a continuous manner, as part of our standard postoperative care. Any abnormalities found will be promptly assessed and described in the patient's medical records. Once the patient is discharged it is very unlikely that any of the study drugs or procedure will cause any abnormalities. Despite this fact, patients will be asked to contact the hospital in case they feel anything unusual. Definitions and examples of the standard or known adverse events associated with cryoablation is tingling, burning sensation, etc., will be presented to the patient for reference. Patients will be also assessed on the above items on their postoperative clinic visits. In addition, emergency contact information of the office in order to speak to someone regarding documentation of these adverse events will be provided. If need be, an immediate unscheduled visit shall be arranged if the patient so desires. The PI will review AE as they occur, changes to the study design or drug use will be determined on an ongoing basis.

XIV. STATISTICAL ANALYSIS PLAN

A. Primary Outcomes

NPS measures will be plotted for each subject over the initial third to fifth postoperatively and the area under the curve (AUC) integrated to produce a cumulative numeric pain score. The primary endpoint will be measured by a statistical comparison of AUC between the groups, using a Wilcoxon rank-sum test. Randomization is expected to balance the groups with respect to preoperative risk factors.

B. Secondary Outcomes

Cumulative dose of opioid medication will be assessed as the sum of morphine doses dispensed by PCA pump during the admission. In addition, we will evaluate the amount of opioid usage using morphine milligram equivalences.²² This will be compared by unpaired t test. We will also evaluate for the opioid prescription need at the time of discharge, and will be compared by chi-square test. Length of hospital stay will be transformed to log scale to normalize the distribution if necessary and will be compared between groups by an appropriate unpaired statistic. Attainment of physical therapy goal that justifies discharge from inpatient physical therapy within 72 hours will be assessed by an appropriate contingency table test.

C. Sample Size Determination

This is a pilot study to prove the feasibility of intercostal nerve cryoablation in patients undergoing the descending/thoracoabdominal aortic aneurysm repair with thoracoabdominal incision.

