There is a small increased risk to the patients by participating in the study in addition to a possible chance of breach in patient confidentiality as the study involves evaluation of an FDA-approved device. As detailed in the informed consent, the subjects are at risk of developing adverse effects from cryoablation, abdominal muscle bulging or sympathetic nerve paresis. Patients will be offered standard optimal medical therapy options, even if that will culminate in withdrawal from the study. In addition, there is risk of an unintentional disclosure of personal health information.

Benefits to participants

The patients stand to receive no direct benefit from the study. However, in the event our results endorse the published reports of reduction in postoperative pain by cryoablation, the group of patients receiving it might be indirectly benefitted through participation.

XVI. STUDY TIMELINE

Considering our group's monthly average for the given procedures and the enrollment rates, drop-outs and withdrawal, and interim analyses we estimate recruitment of our sample size will take 6 months. Once the follow-up of all enrolled participants is finished, data will be analyzed and published. The following is a chronological estimate of the stages:

Stage 1: Patient screening and enrollment 0 - 6 months

Stage 2: Follow-up up to 180 days from the last patient enrolled (0 – 12 months)

Stage 3: Data collection and analysis 1 month

Stage 4: Presentation and publication period (at the end of data analysis)

XVII. QUALITY CONTROL AND ASSURANCE

The PI will be responsible for monitoring the progress and safety of this pilot trial. Any serious or unanticipated events will be reported in a timely manner to the CPHS.

XVIII. CONFLICT OF INTEREST

There is no relationship between the principal investigator or any other research staff member and AtriCure Inc. The 10 probes are provided from the AtriCure Inc. for the current study.

XIX. FUTURE PUBLICATION AND PRESENTATION

The results of this study will be analyzed and published after the approval of the principal investigator and biostatistician in a peer-reviewed scientific journal and/or presented at an international/national scientific conference or meeting regardless of outcome. The publication will acknowledge members of the study research group for their contributions and will maintain patient data protection.

XX. REFERENCES

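### Section XIII treats procedure-related harm after discharge as very unlikely, yet the plan lists nerve harms that may appear later and does not fix how they are asked about at days 30 and 180 or compared by arm

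*Combined protocol and SAP*

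**What the plan says.** Section XIII (Adverse Event Reporting) gives the premise for safety follow-up after discharge: "Once the patient is discharged it is very unlikely that any of the study drugs or procedure will cause any abnormalities". Shortly before that it says that "allodynia like-pain after the degeneration of the affected nerve is reported after cryoablation of the nerve", and adds that this is often tied to the thoracotomy and is not specific to cryoablation. The known events used as examples for patients are described as "tingling, burning sensation, etc., will be presented to the patient for reference". Section XV.C (Risk/Benefits) says that "the subjects are at risk of developing adverse effects from cryoablation, abdominal muscle bulging or sympathetic nerve paresis".

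Section XIII provides three routes for collecting harms after discharge:

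- Patients are told to report unwanted effects throughout the study and to contact the hospital if they notice anything unusual.
- They receive a contact for emergencies and can have an unscheduled visit.
- "Patients will be also assessed on the above items on their postoperative clinic visits". The items meant are adverse effects, vital signs, wound healing, scarring and cardiac monitoring.

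Section XII.7 (Follow-up) is the dated schedule. Item vii reads "30 days after the procedure, the BPI and 5-point scale analgesia satisfaction survey will be assessed". The last item, labelled xiii, reads "Final visit, 180 days after procedure, the BPI and 5-point scale analgesia satisfaction survey will be performed". Neither mentions adverse effects.

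**The concern.** The text that sets expectations for safety follow-up plays down harm after discharge, while other text describes harms that could arise then. The two contacts that every patient is due to have after discharge are not described as asking about those harms. What remains is a general assessment at visits without dates, plus whatever patients volunteer.

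Two things are at stake. The first is completeness: a general enquiry at an unspecified time can miss a harm that a direct question would find. The second is comparability. The plan asserts that allodynia-like pain is not specific to cryoablation. The randomised control arm can test that assertion, but a clear answer needs the same questions, at the same times, in both arms. Under Section XII the surgical team knows the allocation from wound closure, and the plan does not say who makes the clinic assessments or whether they are blinded. Open-ended questioning could therefore differ between arms. The pilot is meant to inform a larger randomised study (Section VI), so its harm data will be looked at.

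**Working it through.** The plan states no harm rate and no safety figure, so there is nothing to reproduce. The check is mainly a comparison of texts.

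**Step 1. Does the post-discharge sentence fit the harms listed?**

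| Harm | Where listed | Timing in the documents | Fit with "Once the patient is discharged it is very unlikely that any of the study drugs or procedure will cause any abnormalities" |
|---|---|---|---|
| Allodynia-like pain | XIII | Follows nerve degeneration; no interval given | In conflict: the wording implies delay |
| Muscle bulging, sympathetic paresis | XV.C | None given | Hard to square, but onset after discharge is an inference |
| Tingling, burning | XIII | None given | Onset after discharge is an inference |

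**Step 2. What is asked, and when?**

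| Route | Covers adverse effects? | Dated? | Nerve harms named? |
|---|---|---|---|
| Clinic visits (XIII) | Yes, in general terms | No | No |
| Volunteered reports (XIII) | Yes | Any time | Examples shown to patients |
| Days 30 and 180 (XII.7) | Not stated | Yes | No; BPI and satisfaction only |

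Section VII describes the BPI as measuring pain and its effect on daily life. It could register painful sequelae, though not as an adverse event. Nothing in that description covers bulging or paresis.

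**Step 3. Is a comparison of harms planned?** Section VIII lists no safety outcome, and Section XIV contains no safety analysis. Section XIII sends abnormalities to the medical record.

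**Step 4. Illustration only.** Assume 10 cryoablation patients: the total is 20 in two groups, and the allocation ratio is not stated. Let *p* be the true rate of a late harm and *c* the fraction of cases recorded. Both are assumptions. Then

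P(at least one case recorded) = 1 − (1 − *pc*)^10.

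| *p* | *c* = 1 | *c* = 0.5 | *c* = 0.25 |
|---|---|---|---|
| 10% | 1 − 0.90^10 = 65% | 1 − 0.95^10 = 40% | 1 − 0.975^10 = 22% |
| 20% | 1 − 0.80^10 = 89% | 1 − 0.90^10 = 65% | 1 − 0.95^10 = 40% |
| 30% | 1 − 0.70^10 = 97% | 1 − 0.85^10 = 80% | 1 − 0.925^10 = 54% |

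For uneven capture, suppose the true rate is 20% in both arms, with *c* = 1 in one and 0.5 in the other. The expected recorded counts are 10 × 0.2 × 1 = 2 and 10 × 0.2 × 0.5 = 1, a difference produced by recording alone.

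With zero events in 10 patients, the upper limit of the exact two-sided 95% interval is 1 − 0.025^(1/10) = 31%. This limit comes from the sample size and would be the same under complete capture.

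**The case against.** The strongest reply is that active collection after discharge is already planned, in the same paragraph as the disputed sentence: adverse effects head the list of items assessed at clinic visits. That stands. A reader might infer from the schedule that post-discharge harms rest on volunteered reports alone; the documents do not support this. The disputed sentence does not itself restrict data collection, since the safeguards follow directly after it.

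The schedule entries for days 30 and 180 also do not exclude adverse event questions. Day 180 is called a visit and may be one of the clinic visits meant in Section XIII. The case report form is not among the documents, so specific nerve items on it cannot be ruled out. This too stands. What can be shown is a missing link between sections, not that nobody will ask.

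The BPI is given alike to both arms at both contacts, so the harm with the clearest claim to be delayed, allodynia-like pain, is partly covered. Patients are blinded, which limits bias in what they volunteer. Both points narrow the concern. They do not reach bulging or paresis, and they do not settle whether clinicians' questioning is even between arms.

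Finally, a reader might infer that late harms will be under-counted by a known amount, or that the 31% limit is a cost of this gap. Neither follows. The rates and capture fractions in the illustration are assumed, and the 31% limit reflects 10 patients.

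**Conclusion.** The point holds in a limited form. The post-discharge sentence in Section XIII conflicts with the allodynia-like pain described in that section and is hard to square with the bulging and sympathetic paresis in Section XV.C. Clinic-visit assessment exists, but it is undated, general and not tied to days 30 and 180, and no comparison of harms by arm is planned. Late nerve harms may therefore be captured incompletely or unevenly.

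The size of any under-count cannot be computed from the documents. The illustration shows only how quickly the chance of seeing a single case falls in a group of 10 when capture is partial; it does not estimate what will happen in this trial. It rests on 1:1 allocation and on assumed rates and capture fractions. The change is worth making because it costs little and lets the control arm test the plan's own statement about allodynia.

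**What to change.** 1. Reconcile the post-discharge sentence in Section XIII with the harms listed in that section and in Section XV.C.
2. In Section XII.7, item vii and the item labelled xiii, add fixed yes/no questions on the harms that the plan itself lists: allodynia-like or burning pain, tingling, abdominal muscle bulging, and signs of sympathetic nerve paresis. Use the same wording in both arms, and record the answers on the case report form.
3. State whether the day 30 and day 180 contacts count as the clinic visits meant in Section XIII.
4. In Section XIV, add a table of counts by arm with exact 95% confidence intervals, and note that with about 10 patients per arm they will be wide.

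The cost is a few questions at two contacts that already take place, and one table. The recorded number of adverse events will probably rise. Sample size and treatment do not change.
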